## **9.0 Data and Specimen Banking**

*9.1 If data or specimens will be banked for future use, describe where the data/specimens will be stored, how long they will be stored, how the data/specimens will be accessed, and who will have access to the data/specimens.*

*Response:* Data will be stored on a password-protected computer in a locked office. The principal investigator will have access to the data for data entry and analysis. Biological specimens collected during the MMTT will be stored in -80°C freezer at Jacobs School of Medicine, 5th floor. Only [name] or research assistants will have access to these specimens. Data will be stored until study completion. Samples will be stored until study completion.

*9.2 List the data to be stored or associated with each specimen.*

*Response:* Data will be stored with subject identifier number. Specimens will have recorded subject identifier, as well as time point during MMTT, and date of collection.

*9.3 Describe the procedures to release data or specimens, including: the process to request a release, approvals required for release, who can obtain data or specimens, and the data to be provided with specimens.*

*Response:* No data will be released.

## **10.0 Data Management**

*10.1 Describe the data analysis plan, including any statistical procedures.*

*Response:* For statistical purposes, the **primary endpoint** of the study is to detect a difference between untreated and treated periods in the change from baseline in mean weekly blood glucose concentrations. The statistical analysis will be carried out using analysis of variance (ANOVA) and tested at the 0.05 level. The results will be computed as mean±SD.

The secondary end points based on glycemic changes will include the difference from baseline in standard deviations of the mean weekly glucose concentrations, mean fasting blood glucose concentrations, the duration of time spent in hyperglycemia ( $>150\text{mg/dL}$ ,  $>200\text{mg/dL}$ ,  $>250\text{mg/dL}$ ) and hypoglycemia ( $<70\text{mg/dL}$ ,  $<40\text{mg/dL}$ ), and insulin dosage. A reduction in the area under curve following the meal will constitute another secondary end point. Within subject comparisons of the magnitude of change from baseline will also be made for these glycemia related secondary endpoints using student's t-test. Comparisons for these and the primary endpoints will also be made using the paired t-test or Wilcoxon's test for paired data for each subject. Additional secondary end-points of the study will be change from baseline in 1) mean weekly blood glucose 2) glucagon area under the curve concentrations following meal challenge 3) change in daily insulin dose (total dose and units/kg) 4) caloric intake based on 4 day food records and 5) change in serum adiponectin and CRP levels before and after initiation of liraglutide treatment. The relation between change in postprandial sugars, glucagon, and total daily insulin dose will be studied by regression analysis to evaluate the relative contribution of each of these parameters to the improvement in post-prandial blood sugars

*10.2 Provide a power analysis.*

*Response:* A previous study (5) in adults with well-controlled diabetes demonstrated that liraglutide treatment decreased mean weekly blood sugars by 22 mg/dL. Based on these results, *a priori* power analysis indicates that 9 subjects will need to be enrolled in the study to detect a change in mean weekly blood sugars of  $22 \pm 20\text{ mg/dL}$  between untreated and treated periods with 80% power and alpha error of 0.05 (paired t-test). We will enroll up to 12 subjects for this study.

*10.3 Describe the steps that will be taken to secure the data (e.g., training, authorization of access, password protection, encryption, physical controls, certificates of confidentiality, and separation of identifiers and data) during storage, use, and transmission.*

*Response:* All primary data collection tools will be stored in [name] office. All personal information, signed consents/assents and patient blood sugar logs/food diaries will be stored in a locked filing cabinet in principal investigator's locked office. Data will be entered into a password protected Excel Spreadsheet. Access to the computer system is also password protected and only members of the study team will have access to the electronic data. All members of the team have completed CITI and GRP training. Data will not be transmitted.

*10.4 Describe any procedures that will be used for quality control of collected data.*

Response: [name] will be responsible for review of data on a regular basis to ensure that collected data is being entered correctly.

*10.5 Describe how data and specimens will be handled study-wide:*

Response: Data will be entered electronically in a timely manner. Downloads of meters/pumps are scanned into the medical record as part of standard of care.

*10.6 What information will be included in that data or associated with the specimens?*

Response: See data collection tool. Each subject will be assigned a unique study identification number.

*10.7 Where and how data or specimens will be stored?*

Response: All personal information, signed consents/assents and patient blood sugar logs/food diaries will be stored in a locked filing cabinet in principal investigator's locked office. Data will be stored on a password-protected computer in [name] office.

*10.8 How long the data or specimens will be stored?*

Response: Data will be stored for 5 years after the completion of the study.

*10.9 Who will have access to the data or specimens?*

Response: Study data will be stored on a password-protected computer that is limited to the principal investigator and co-investigators.

*Who is responsible for receipt or transmission of the data or specimens?*

Response: [name]

*10.10 How data and specimens will be transported?*

Response: Data will be stored on password-protected computer. Data will not be transported.

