two drugs – exenatide (BID) and liraglutide (QD) are administered subcutaneously. They have been demonstrated to improve glycemic control in this population and, in some individuals, lead to sustained weight loss.

This study aims to determine whether acute exposure to liraglutide decreases the mean weekly blood glucose levels in adolescents with T1DM. In addition, we will determine whether liraglutide decreases glucose excursions following a meal challenge. *The overall hypothesis to be tested is that short-term exposure (7 days) to liraglutide improves glycemic control in adolescents/young adults with T1DM treated with continuous subcutaneous insulin infusion.*

**Specific Aim 1:** Determine whether liraglutide decreases the mean weekly blood glucose levels in adolescents/young adults with T1DM. *Hypothesis: Mean weekly blood glucose will decrease when liraglutide is used as an adjuvant therapy to insulin in individuals with T1DM.* Subjects will wear continuous glucose monitors to measure interstitial glucose as a surrogate for blood glucose. The CGM will be worn for 7 days pre- and post- daily liraglutide treatment. Data will be downloaded and mean weekly blood sugars will be determined.

**Specific Aim 2:** Determine whether liraglutide treatment decreases blood glucose excursion during mixed meal tolerance test in adolescents/young adults with T1DM. *Hypothesis: Post-prandial blood glucose excursions are attenuated with liraglutide treatment.* Mixed meal tolerance tests will be performed with and without pre-treatment with liraglutide. Blood glucose levels will be measured at set time points during the test and blood glucose excursions as well as blood glucose AUC in response to the meal challenge will be calculated.

**Specific Aim 3:** Determine whether glucagon secretion decreases during mixed meal tolerance test in subjects treated with liraglutide. *Hypothesis: Glucagon secretion following a meal challenge is suppressed in response to liraglutide treatment.* Serum samples will be drawn during mixed meal tolerance test performed with and without pre-treatment with liraglutide. Glucagon will be measured by ELISA and glucagon secretion AUC will be calculated.

**Specific Aim 4:** Determine whether liraglutide treatment leads to a reduction in total daily insulin dose.

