## 6.0 Study Timelines

6.1 *Describe the duration of an individual subject's participation in the study.*

Response: The total duration of time for participation is 2 weeks. This study involves three visits.

6.2 *Describe the duration anticipated to enroll all study subjects.*

Response: 4 years

6.3 *Describe the estimated date for the investigators to complete this study (complete primary analyses)*

Response: 60 months

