## 7.0 Study Endpoints

7.1 *Describe the primary and secondary study endpoints.*

Response: For statistical purposes, the **primary endpoint** of the study is to detect a difference between untreated and treated periods in the change from baseline in mean weekly blood glucose concentrations. The statistical analysis will be carried out using

analysis of variance (ANOVA) and tested at the 0.05 level. The results will be computed as mean $\pm$ SD.

The secondary end points based on glycemic changes will include the difference from baseline in standard deviations of the mean weekly glucose concentrations, mean fasting blood glucose concentrations, the duration of time spent in hyperglycemia ( $>150\text{mg/dl}$ ,  $>200\text{mg/dl}$ ,  $>250\text{mg/dl}$ ) and hypoglycemia ( $<70\text{mg/dl}$ ,  $<40\text{mg/dl}$ ), and insulin dosage. A reduction in the area under curve following the meal will constitute another secondary end point. Within subject comparisons of the magnitude of change from baseline will also be made for these glycemia related secondary endpoints using student's t-test. Comparisons for these and the primary endpoints will also be made using the paired *t*-test or Wilcoxon's test for paired data for each subject. Additional secondary end-points of the study will be change from baseline in 1) mean weekly blood glucose 2) glucagon area under the curve concentrations following meal challenge 3) change in daily insulin dose (total dose and units/kg) 4) caloric intake based on 4 day food records and 5) change in serum adiponectin and CRP levels before and after initiation of liraglutide treatment. The relation between change in postprandial sugars, glucagon, and total daily insulin dose will be studied by regression analysis to evaluate the relative contribution of each of these parameters to the improvement in post-prandial blood sugars.

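### Do the ANOVA without a stated model and the undefined change from baseline leave the primary comparison open?

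*Combined protocol and SAP*

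**What the plan says.** Sections 7.1 and 10.1 carry the same text. The aim of the primary endpoint is to "detect a difference between untreated and treated periods in the change from baseline in mean weekly blood glucose concentrations". On the test, the text reads "The statistical analysis will be carried out using analysis of variance (ANOVA) and tested at the 0.05 level", with no factors, subject term or error term. The next paragraph adds: "Comparisons for these and the primary endpoints will also be made using the paired t-test or" the Wilcoxon test for paired data. It then lists the same variable again: "Additional secondary end-points of the study will be change from baseline in 1) mean weekly blood glucose".

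Section 10.2 sizes the trial for a change of 22 ± 20 mg/dL, "between untreated and treated periods with 80% power and alpha error of 0.05 (paired t-test"). It asks for 9 subjects and allows enrolment of up to 12.

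The schedule has two glucose weeks. Specific Aim 1 (section 1.3) states: "The CGM will be worn for 7 days pre- and post- daily liraglutide treatment". Section 6.1 states: "The total duration of time for participation is 2 weeks". The variable lists in section 7.1 include mean weekly glucose at Visits 2 and 3 but not at Visit 1. Section 8.1 describes the trial as an unblinded, within-subject pilot.

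**The concern.** Read literally, the endpoint cannot be computed for the untreated week. That week is the only scheduled baseline, and its change from itself is zero. The test is open as well. The word ANOVA could mean a within-subject model, a one-way model that ignores pairing, or an ANOVA on change scores with zeros entered for the untreated week. Two further tests are named with no rule for choosing between them, and the trial is powered on only one of them.

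The stakes would be real if these readings were live. The zeros reading is anti-conservative, and the one-way reading can lose much of the planned power. The trial is unblinded, and section 9.1 gives the principal investigator access to the data for entry and analysis, so a choice of test could be made after the results are visible.

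**Working it through.** **Inputs.** From section 10.2: difference 22 mg/dL; SD 20 mg/dL, read as the SD of the within-subject difference; alpha 0.05, taken as two-sided; n = 9, with a maximum of 12. The correlation between the two weekly means is not given, so a range is assumed where it is needed.

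**1. The plan's own figure.** Standardised effect d = 22/20 = 1.10. Power comes from the noncentral t distribution with n − 1 degrees of freedom and noncentrality d√n.

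| n | d√n | critical t | power |
|---|---|---|---|
| 8 | 3.11 | 2.365 | 76.1% |
| 9 | 3.30 | 2.306 | 82.3% |
| 12 | 3.81 | 2.201 | 93.3% |

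Nine is the smallest n that reaches 80%, so the stated figure is reproduced.

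**2. Within-subject ANOVA with two periods.** Let D be the mean difference and s the SD of the differences. The period mean square is nD²/2 and the error mean square is s²/2. Hence F = nD²/s² = t², on 1 and n − 1 degrees of freedom. The p-value and the power are those of the paired t-test, so under this reading 10.1 and 10.2 agree exactly.

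**3. Paired t-test versus exact Wilcoxon signed-rank.** Simulation with normal differences, 400,000 trials per setting:

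| | n = 9 | n = 12 |
|---|---|---|
| Wilcoxon power | 76% | 91% |
| The two tests disagree at 0.05, true difference 22 | 7.0% | 3.1% |
| of which only the t-test is significant | 6.4% | 2.7% |
| Type I error if either may count | 5.3% | 5.4% |

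Other runs put the either-test error at n = 9 at 5.2%. Much of the disagreement comes from the discreteness of the exact Wilcoxon test, whose attainable two-sided level is 3.9% at n = 9 and 4.2% at n = 12.

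**4. Zeros for the untreated week.** One group has variance zero, so the pooled variance is s²/2 and the standard error is √(2·(s²/2)/n) = s/√n. The statistic equals the paired t but is referred to 2n − 2 degrees of freedom. True alpha is 2P(t₈ > 2.120) = 6.7% at n = 9 and 2P(t₁₁ > 2.074) = 6.2% at n = 12.

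**5. One-way ANOVA ignoring pairing.** With the SD of the difference held at 20, the SD of a weekly mean is 20/√(2(1 − ρ)). Simulated results for assumed ρ:

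| ρ | 0 | 0.3 | 0.5 | 0.7 | 0.8 |
|---|---|---|---|---|---|
| power, n = 9 | 87% | 77% | 62% | 36% | 18% |
| power, n = 12 | 95% | 90% | 80% | 53% | 29% |
| type I error, n = 9 | 5.0% | 2.3% | 1.0% | 0.24% | 0.07% |

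For any positive correlation this reading is conservative and does not add false positives.

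**6. Which reading do the documents support?** Section 8.1 states a within-subject design. Aim 1 sets a pre-treatment week against a treatment week. Section 10.1 names tests for paired data for the primary endpoint, and 10.2 uses a paired t-test on untreated versus treated. Steps 1 to 3 are consistent with all four places. Step 5 contradicts the design. Step 4 requires an analyst to enter a constant column and treat it as data.

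**The case for a change.** The strongest argument for acting is that an intention one can infer is not pre-specification. In an unblinded study analysed by those who run it, the deciding test should be written down before the data are seen, and doing so would cost only a few words in 7.1 and 10.1. It is also true that no section says which test decides or defines a baseline before the untreated week. The exact Wilcoxon test at 9 subjects would fall short of the planned 80% power.

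Those facts stand, but they carry little weight here. The freedom that remains is between two tests of the same paired difference. Choosing after the fact moves alpha by less than half a percentage point above 5%. The shortfall under Wilcoxon is about 6 percentage points at n = 9 and is gone at the permitted 12. The repeated secondary entry is the same variable and the same contrast, so it adds no hypothesis. The trial is an unfunded pilot, and section 14.1 looks to later randomised, placebo-controlled studies to test efficacy.

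**Conclusion.** The wording is loose but the analysis is recoverable. The primary comparison is the treated-week mean minus the untreated-week mean within each subject. On that reading the ANOVA and the paired t-test are the same test, and the stated sample size is correct, with 82.3% power at 9 subjects and 93.3% at 12. The realistic consequence of what is left unsaid is a type I error of about 5.2 to 5.4% if either paired test may count, or about 76% power at 9 subjects if Wilcoxon alone is used. These figures assume normally distributed differences, a two-sided 0.05 level and an SD of the difference of 20 mg/dL. The alpha of 6.2 to 6.7% and the power as low as 18% belong to readings that the design does not support, and the low power also needs a high correlation that the documents do not give. The gap is one that a competent analyst fills in the same way as 10.2 does, so no change to the plan is called for.

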#### **Visit 1 Screening Day (day 0):**

- Review the subject's medical history and family medical history
- Review subject's blood sugars and insulin pump settings
- Measure height, weight, blood pressure and heart rate.
- The principal investigator will perform a physical exam.
- If hemoglobin A1c level is not recorded in the medical record within 2 weeks of visit 1, this test will be performed.
- Record mean total daily insulin dose (previous 72 hours) from insulin pump.
- Subjects will be advised to wear his/her continuous glucose monitor (CGM) for the next two weeks, changing sites as indicated by the manufacturer.
- For subjects who do not have a CGM, we will insert the Abbott Freestyle Libre Professional Device. This device will monitor glucose levels throughout the entire study period. Subjects will be advised to check blood sugars at least 4 times per day and at any occasion when symptoms of hypoglycemia develop.
- Subjects will be asked to keep a record of any episodes of hypoglycemia.
- Subjects will be asked to keep a 4 day food record (three days, 1 weekend day).
- Subjects will be advised to follow their usual diabetes care plan with respect to carbohydrate counting, diet and exercise.

**Visit 2 (Day 7):** Subjects will come fasting for this visit. They will bring the food records and diary of hypoglycemia to this visit. This visit will take approximately 4 hours. At this visit, the following procedures will be performed:

- Records of blood sugars and CGM data will be obtained from subjects wearing personal CGMs
- Subjects wearing the Freestyle LibrePro system will continue wearing the device unless it became dislodged during the study. A new device will be placed in this case.
- Blood sugars and insulin pump settings will be reviewed.
- Record mean total daily insulin dose (previous 72 hours) from insulin pump.
- A Mixed Meal Tolerance test will be performed (see below)

- Insulin pump settings will be adjusted to decrease the risk of hypoglycemia during liraglutide treatment. Basal rates will be decreased by 25% and meal boluses will be decreased by 33%.
- The first dose of liraglutide will be given at the study site. Subjects will be given 0.6 mg subcutaneously. Subjects will be taught how to use the delivery device at this visit.
- Subjects will be advised to take 0.6 mg of liraglutide subcutaneously every morning at about the same time.

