- Subjects will be given a diary and be asked to record any episodes of hypoglycemia, as well as any other side effects such as nausea, decrease in appetite, and other problems.
- Subjects will be asked to keep a 4 day food record (three days, 1 weekend day).
- Subjects will be provided with contact information for the principal investigator in case of any problem or untoward side effect. They will be asked to notify the study staff for persistent low blood sugar (BS < 70 mg/dL), persistent high blood sugar (BS > 250 mg/dL), or urine ketones.
- Subjects will be advised to return to clinic in 7 days.

**Visit 3 (Day 14):** This is the final study visit. Subjects will come fasting for this visit. The subject will not take liraglutide prior to coming to this visit but will bring the study drug to the visit. Subjects will bring the food records and diary of hypoglycemia to this visit. This visit will take approximately 4 hours. At this visit, the following procedures will be performed:

- Records of blood sugars and CGM data will be obtained.
- Freestyle LibrePro device will be removed and data obtained.
- Blood sugars and insulin pump settings will be reviewed
- Record mean total daily insulin dose (previous 72 hours) from insulin pump.
- Liraglutide (0.6 mg subcutaneously) will be administered 45 minutes prior to the Mixed Meal Tolerance Test
- A Mixed Meal Tolerance test will be performed (see below).
- All study drug will be returned.
- Subjects will be advised to resume previous basal rates and carbohydrate ratios within 48 hours of final study visit.

**Mixed Meal Tolerance Test (MMTT).** This test will be done at Visit 2 and Visit 3. The MMTT is a test to measure blood sugar levels in response to a meal and the amount of glucagon that is produced in response to changes in blood sugar. Prior to the test, a catheter will be placed to reduce the number of needle sticks during the test. Subjects will drink 240 ml of a high protein nutrition drink (BOOST). An appropriate amount of insulin for the carbohydrate intake of the meal challenge will be administered via insulin pump to taking the drink. Blood will drawn once before the meal and 8 times during the meal over 3 hours. The total amount of blood that will be drawn is ~ 20 teaspoons (100 mL).

The following parameters will be drawn for measurement during the MMTT

- Blood Glucose
- Glucagon
- Serum inflammatory mediators

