Glucagon-like peptide 1 is an incretin hormone that is released in response to ingestion of food. Long-acting GLP-1 analogues and drugs which inhibit the metabolism of GLP-1 are FDA-approved as adjuvant therapy for the treatment of Type 2 diabetes. These drugs are currently not approved for use in the T1DM population. Individuals treated with GLP-1 analogues are at increased risk for hypoglycemia. It is recommended that patients treated with insulin secretagogue therapies (ie sulfonylureas), have their secretagogue dose decrease when GLP-1 analogue therapy is initiated. In this study, subjects have T1DM and are reliant on insulin for blood sugar control. In order to decrease the risk of hypoglycemia in this population, subjects will be counseled to decrease their basal insulin rates by 25% and their bolus insulin coverage for carbohydrates by 30% during the seven days when they are receiving liraglutide. All study subjects will be advised to check their blood sugar if they experience any symptoms consistent with hypoglycemia. They will be asked to contact the study team for persistent hypoglycemia while taking liraglutide. In addition, because insulin doses will be decrease significantly when liraglutide is initiated, there is the risk that subjects will experience hyperglycemia and may develop ketonuria. Subjects will be advised to contact the study team for persistent hyperglycemia and/or presence of urine ketones. The insulin dose will be increased to address this concern.

The most common side effects experienced by adults taking liraglutide include headache, nausea, and diarrhea. Nausea is most common when first starting liraglutide but generally decreases with time. Subjects may also feel less hungry while taking liraglutide. We will monitor for these and additional side effects during the study.

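### The planned regression cannot show how much change in glucagon and change in total daily insulin dose each contributed to the post-meal glucose improvement

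*Combined protocol and SAP*

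**What the plan says.** The same sentence appears in 7.1 (Study Endpoints) and 10.1 (data analysis plan): "The relation between change in postprandial sugars, glucagon, and total daily insulin dose will be studied by regression analysis", with the purpose "to evaluate the relative contribution of each of these parameters" to the improvement in post-meal glucose. It follows the secondary endpoints and is not among the exploratory aims listed in the Background section. Neither section gives a model, a covariate list or a sample-size basis for it. The power analysis in 10.2 covers only the paired change in mean weekly glucose.

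Five other provisions bear on it:

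- **Design (8.1).** A pilot, unblinded, within-subject study with no parallel control.
- **Insulin at Visit 2 (8.2).** At the visit where the first liraglutide dose is given: "Basal rates will be decreased by 25% and meal boluses will be decreased by 33" percent. Section 13.1 describes the same step differently; subjects are counseled to "decrease their basal insulin rates by 25% and their bolus insulin coverage for carbohydrates by 30" percent.
- **Later changes (13.1).** On persistent hyperglycemia or ketones: "The insulin dose will be increased to address this concern".
- **Insulin dose as recorded (8.2).** "Record mean total daily insulin dose (previous 72 hours) from insulin pump". Specific Aim 4 instead speaks of seven days before and after the start of treatment.
- **Insulin at the meal test (8.2).** "An appropriate amount of insulin for the carbohydrate intake of the meal challenge will be administered via insulin pump". The amount is not stated, nor whether the reduced bolus setting applies at Visit 3.

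**The concern.** A regression can speak to contribution only if the explanatory variable varies for reasons separate from the treatment and from the outcome. Change in total daily dose fails on both counts. Its main component is assigned to everyone together with liraglutide. A later component is triggered by glucose itself. It also measures a different exposure from the insulin that covers the test meal.

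The stake is interpretive. Section 14.1 says the results may be used to develop longer randomized, placebo-controlled studies. A statement that glucagon, or insulin, accounts for a given share of the improvement could be carried into those designs without support. As this is a secondary analysis outside the exploratory list, nothing in the plan warns the reader to discount it.

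**Working it through.** **1. The plan's own figure.** Inputs from 10.2: change 22 mg/dL, read with SD 20 mg/dL, alpha 0.05, 80% power, paired t-test. Two-sided testing is assumed because sidedness is not stated. The standardized change is 22/20 = 1.10. Noncentral-t power is 76.1% at n=8, 82.3% at n=9 and 93.3% at n=12. The stated 9 is therefore reproduced, but it concerns mean weekly glucose and says nothing about the regression.

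**2. Size of the imposed insulin cut.** If settings are followed and intake and bolusing do not change, the cut as a fraction of total dose is 0.25b + c(1 - b). Here b is the basal share and c the bolus cut. The documents give no basal share; 30% to 70% is assumed.

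| Basal share b | c = 33% (8.2) | c = 30% (13.1) |
|---|---|---|
| 30% | 0.075 + 0.231 = 30.6% | 0.075 + 0.210 = 28.5% |
| 50% | 0.125 + 0.165 = 29.0% | 0.125 + 0.150 = 27.5% |
| 70% | 0.175 + 0.099 = 27.4% | 0.175 + 0.090 = 26.5% |

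Under these conditions the assigned part differs between subjects by 3.2 or 2.0 percentage points. On the plan's own scale of total units it varies more: a 29% cut is 11.6 units from an illustrative baseline of 40 units and 23.2 from 80. That spread mostly reflects baseline dose.

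**3. What the regression can see.** The part of the insulin cut common to all subjects starts with the drug. Without a control arm it cannot be separated from the drug's average effect. What remains to be regressed on is variation from intake, basal/bolus split, baseline dose and later adjustments. The adjustments made for hyperglycemia are consequences of glucose, so they would tend to link higher insulin with higher glucose.

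**4. Precision with two predictors (glucagon and total daily dose).**

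- Residual degrees of freedom, n - 3: 6 (n=9) or 9 (n=12).
- Expected R-squared with no association, 2/(n - 1): 2/8 = 0.25 or 2/11 = 0.18. The 95th percentiles are 0.63 and 0.49.
- 95% CI for an observed partial correlation of 0.5 (Fisher z, standard error 1/√(n - 4)): 0.549 ± 1.96/√5 gives -0.32 to 0.89 at n=9; 0.549 ± 1.96/√8 gives -0.14 to 0.85 at n=12.
- Smallest observed partial correlation reaching p < 0.05, t/√(t² + df): 0.71 (n=9) or 0.60 (n=12).

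**5. Precision of the share itself.** Simulation, 10,000 runs per setting, with two truly equal and uncorrelated predictors and an assumed true R-squared of 0.5. The share of R-squared is averaged over order of entry. The estimated share of one predictor has a 95% range of about 2% to 98% at n=9 and 3% to 97% at n=12. With predictor correlation 0.5 it is still about 6% to 94% at n=12.

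**The case against.** **The protocol sets pump settings, not delivered dose.** A reader might infer that insulin dose is fixed and so has no spread to analyze. The documents do not support that. Delivered dose depends on carbohydrate eaten and boluses given, both collected under 8.5. Exploratory Aim 2 expects intake to fall, 13.1 allows increases, and 10.1 names total dose and units/kg rather than percent change. The narrow range in step 2 holds only under its stated conditions. This objection stands, and the point does not depend on a constant predictor.

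**A predictor without spread would not spoil the glucagon estimate.** Also correct: the model would then be roughly glucagon alone. The glucagon coefficient is at risk through reverse causation, whose size is unknown because the documents do not say how often insulin will be raised.

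**Post-meal glucose appears both as outcome and in the list of parameters.** This is loose wording. The natural reading is glucose improvement as outcome, with glucagon and insulin dose as explanatory variables.

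**The replacement is imprecise too.** True. A simple correlation of 0.5 has a 95% CI of -0.25 to 0.87 (n=9) or -0.10 to 0.83 (n=12). The gain lies in making a smaller claim with its uncertainty shown, not in precision.

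**It is a small pilot with no power claimed for this analysis.** That limits the consequence. It does not justify the wording, since the protocol has an exploratory list and leaves this analysis off it. Nor do the documents say that the result will be reported as an established mechanism; they say only that the relation will be studied and evaluated.

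**Conclusion.** The point holds, as a minor one. The regression cannot evaluate relative contribution for four reasons: the initial insulin change is confounded with liraglutide; later increases are partly a response to glucose; the 72-hour dose is not the meal-test insulin; and 9 to 12 subjects leave the shares almost undetermined. The first three come from the design and would remain with more subjects.

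The size of the imposed cut (27.4% to 30.6%, or 26.5% to 28.5%) rests on the assumed basal share and unchanged intake. The simulated shares rest on the assumed R-squared and predictor correlations. The chance R-squared and the confidence intervals need only the sample size and a two-predictor model. The conclusion is the same under either stated bolus cut, but 8.2 and 13.1 contradict each other and must be reconciled. The primary endpoint and the sample size of 9 are unaffected.

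**What to change.** Make the same edit in 7.1 and 10.1:

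- Delete the relative-contribution wording, and do not use total daily insulin dose as an explanatory variable for attribution.
- Report the association between change in glucagon AUC and change in post-meal glucose AUC, labelled exploratory, with a 95% CI.
- Describe separately, per subject, the protocol-imposed insulin change, any later adjustments, and the insulin units given at each meal test.

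Alongside this, reconcile the bolus reduction between 8.2 and 13.1, and the period over which total daily dose is taken between 8.2 (72 hours) and Specific Aim 4 (seven days).

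The cost is wording, plus recording the meal-test units and adjustments if the data collection tool does not already do so. The plan gives up a mechanistic statement that it could not have supported.
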